### **Tier 2 Events**

Tier 2 parameters will be assessed via point estimates with 95% CIs provided for differences in the proportion of participants with events using the Miettinen and Nurminen method, an unconditional, asymptotic method [Miettinen, O. and Nurminen, M. 1985].

Membership in Tier 2 requires that at least 10% of participants in any treatment group exhibit the event; all other AEs and predefined limits of change will belong to Tier 3. The threshold of at least 10% of participants was chosen for Tier 2 events because the population randomized in this study are in critical conditions and usually experience various AEs of similar types regardless of treatment; events reported less frequently than 10% of participants would obscure the assessment of the overall safety profile and add little to the interpretation of potentially meaningful treatment differences. In addition, Grade 3 to 5 AEs ( $\geq 5\%$  of participants in one of the treatment groups) and SAEs ( $\geq 5\%$  of participants in one of the treatment groups) will be considered Tier 2 endpoints. Because many 95% CIs may be provided without adjustment for multiplicity, the CIs should be regarded as a helpful descriptive measure to be used in safety review, not a formal method for assessing the statistical significance of the between-group differences.

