## 4 STUDY DESIGN

### 4.1 Overall Design

**NOTE: As of Amendment 007-06, lenvatinib and matching placebo have been removed from the study. Participants who remain on treatment will receive open-label**

**pembrolizumab monotherapy, as per protocol. The Second-course Treatment Phase is removed from the study. This section has been updated accordingly.**

The original study design was a randomized, double-blind, active-control with placebo, parallel-group, multisite study of IV pembrolizumab and oral lenvatinib in participants with Stage IV NSCLC and PD-L1 TPS  $\geq 1\%$  who have not had previously received systemic therapy for metastatic disease, whose tumors express PD-L1 with a TPS  $\geq 1\%$ , and in whom EGFR-, ALK-, or ROS proto-oncogene 1 (*ROS1*)-directed therapy is not indicated.

Participants were randomized 1:1 to Arm A (pembrolizumab + lenvatinib) or Arm B (pembrolizumab + matching placebo). Randomization was stratified by site geographic region (East Asia vs non-East Asia), ECOG PS (0 vs 1), and TPS (1%-49% vs  $\geq 50\%$ ). The original study design is depicted in [Figure 1](#) (Initial Treatment Phase).

**As of Amendment 007-06**, lenvatinib and matching placebo have been removed from the treatment arms (Figure 1). All participants remaining on treatment in the study will receive open-label pembrolizumab monotherapy. Treatment with pembrolizumab will continue up to Cycle 35 or until reaching a discontinuation criterion (defined in Section 7.1). Imaging will continue until progression by local investigator has been determined.

Participants will be evaluated with radiographic imaging to assess response to treatment every 9 weeks from randomization through 54 weeks, then every 12 weeks until PD, initiation of a new anticancer regimen, or completion of 35 cycles. All imaging obtained on study will be submitted to the imaging vendor for BICR, which will assess the images using RECIST 1.1 (see Section 8.2.1.5) for determination of OR, PFS, and DOR. After amendment 007-06, imaging obtained on study will be submitted to the imaging vendor but these will not be assessed, similarly, verification of PD is no longer needed before treatment discontinuation. Treatment-based decisions may use site-assessed iRECIST, as described in Section 8.2.1.6, which allows for participants with initial site-assessed PD to continue treatment until PD is confirmed by the site 4 to 8 weeks later.

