### **8.4.1 Time Period and Frequency for Collecting AE, SAE, and Other Reportable Safety Event Information**

All AEs, SAEs, and other reportable safety events that occur after the participant provides documented informed consent but before intervention allocation/randomization must be reported by the investigator if the participant is receiving placebo run-in or other run-in treatment, if the event cause the participant to be excluded from the study, or is the result of a

protocol-specified intervention, including but not limited to washout or discontinuation of usual therapy, diet, or a procedure.

- All AEs from the time of intervention allocation/randomization through 30 days following cessation of study intervention must be reported by the investigator.
- All AEs meeting serious criteria, from the time of intervention allocation/randomization through 90 days following cessation of study intervention or 30 days following cessation of study intervention if the participant initiates new anticancer therapy, whichever is earlier, must be reported by the investigator.
- All pregnancies and exposure during breastfeeding, from the time of treatment allocation/randomization through 120 days following pembrolizumab/placebo or 30 days following cessation of lenvatinib/placebo, whichever occurs last, must be reported by the investigator. If the participant initiates new anticancer therapy following discontinuation of study intervention, the time period for reporting pregnancies and exposure during breastfeeding is reduced to 30 days following cessation of study intervention.

Exception: A positive pregnancy test at the time of initial screening is not a reportable event unless the participant has received study intervention.

- Additionally, any SAE brought to the attention of an investigator at any time outside the time period specified above must be reported immediately to the Sponsor if the event is considered related to study intervention.

Investigators are not obligated to actively seek AEs or SAEs or other reportable safety events in former study participants. However, if the investigator learns of any SAE, including a death, at any time after a participant has been discharged from the study, and he/she considers the event to be reasonably related to the study intervention or study participation, the investigator must promptly notify the Sponsor.

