### 9.5.2 Safety Analysis Populations

Safety analyses will be conducted in the APaT population, which consists of all randomized participants who received at least 1 dose of study intervention. Participants will be included in the treatment group corresponding to the study intervention they actually received for the analysis of safety data using the APaT population. This will be the treatment group to which they were randomized, except for participants who take incorrect study intervention for the entire treatment period; such participants will be included in the treatment group corresponding to the study intervention actually received. Any participant who receives the incorrect study intervention for 1 cycle, but receives the randomized treatment for all other cycles, will be analyzed according to the randomized treatment group, and a narrative will be provided for any events that occur during the cycle for which the participant is incorrectly dosed.

At least 1 laboratory, vital sign, or ECG measurement obtained after at least 1 dose of study intervention is required for inclusion in the analysis of the respective safety parameter. To assess change from baseline, a baseline measurement is also required.

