### **9.12 Extent of Exposure**

Extent of exposure for a participant is defined as number of cycles in which the participant receives the study intervention. Summary statistics will be provided on extent of exposure for the APaT population.

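### Tier 2 adverse events are compared only as crude proportions although observation time depends on treatment duration; adding a time-adjusted comparison is a cheap improvement

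*Combined protocol and SAP*

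**What the plan says.** Section 9.6.2 gives one between-arm method for adverse events: "Tier 2 parameters will be assessed via point estimates with 95% CIs provided for differences in the proportion of participants with events". The intervals are Miettinen-Nurminen intervals. Table 10 and the Section 9.1 summary say the same. Entry to the tier rests on the same crude percentages: "Membership in Tier 2 requires that at least 10% of participants in any treatment group exhibit the event", with a 5% threshold for Grade 3 to 5 events and for serious events. The intervals are described modestly: "the CIs should be regarded as a helpful descriptive measure to be used in safety review". The reason given is multiplicity, not follow-up time. The population is stated in Section 9.5.2: "Safety analyses will be conducted in the APaT population, which consists of all randomized participants who received at least 1 dose of study intervention".

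Section 8.4.1 sets the observation window: "All AEs from the time of intervention allocation/randomization through 30 days following cessation of study intervention must be reported by the investigator". For serious events it runs "through 90 days following cessation of study intervention or 30 days following cessation of study intervention if the participant initiates new anticancer therapy". The earlier of the two dates applies, and serious events considered related are reportable even after that.

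Treatment length is variable. Section 4.1 states: "Treatment with pembrolizumab will continue up to Cycle 35 or until reaching a discontinuation criterion". The criteria in Section 7.1 include progression and unacceptable toxicity.

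On exposure, Section 9.12 says: "Extent of exposure for a participant is defined as number of cycles in which the participant receives the study intervention", with summary statistics only. Nothing in Section 9 links adverse events to time at risk. Kaplan-Meier methods are specified for PFS, OS, duration of response and time to deterioration, but not for adverse events.

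The opening note of Section 9 ends the efficacy analyses but keeps selected safety analyses for the end of the study.

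**The concern.** A participant's window is time on treatment plus a tail, and time on treatment is itself an outcome that may differ between arms. A crude proportion mixes the rate of events with the length of the window. If the combination arm stayed on treatment longer, background events would accumulate there even at an identical monthly risk. If it stopped earlier because of toxicity, a real excess could shrink or vanish in the crude comparison, which is the more serious error for a safety conclusion. The tier thresholds use the same percentages, so follow-up time also affects which events receive an interval at all. Because efficacy analyses have ended, the safety comparison carries much of what the trial will still report.

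**Working it through.** **Plan's own figure.** The plan states no figure for the Tier 2 comparison. The illustration uses the PFS inputs of Section 9.9, so those were checked first: 416 events, hazard ratio 0.7, one-sided alpha 0.0055, 1:1 allocation. By Schoenfeld's formula, power = Φ(½·√416·|ln 0.7| − 2.543) = Φ(3.637 − 2.543) = 86.3%, against 86.5% stated. The inputs are coherent.

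**Inputs.**
- Control PFS (Section 9.9): median 5 months up to 6.5 months, then median 12 months. The hazards are ln 2/5 = 0.139 and ln 2/12 = 0.058 per month.
- Combination PFS: the same hazards multiplied by the hazard ratio.
- Cap on treatment: 35 cycles × 21 days = 735 days; 735/30.4375 = 24.1 months (C).
- Tail: 30 days = 0.99 month (W).
- 310 per arm, from 620 randomised 1:1. The treated population could be slightly smaller.
- Assumptions not in the documents: treatment stops at the PFS event; the event hazard λ is constant and, except where stated, equal in both arms; no administrative cutoff; deaths within the tail ignored.

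**Formula.** With T = min(PFS time, C), the probability of at least one event is 1 − e^(−λW)·E[e^(−λT)], where E[e^(−λT)] = 1 − λ∫₀^C S(t)e^(−λt)dt. For each control risk, λ is solved from the control arm and then applied unchanged to the combination arm.

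**Mean windows.** Control 9.8 months; combination 11.0 months at hazard ratio 0.85 and 12.5 months at 0.7.

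**Crude difference at equal event hazard** (combination minus control). The last column is the chance that the 95% interval excludes zero at hazard ratio 0.7, by a normal approximation to Miettinen-Nurminen; the nominal value is 5%.

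| Control risk | HR 0.85 | HR 0.7 | Interval excludes 0 (HR 0.7) |
|---|---|---|---|
| 10% | +1.2 points | +2.7 points | 18% |
| 20% | +2.2 points | +4.9 points | 31% |
| 30% | +3.1 points | +6.7 points | 42% |
| 50% | +3.8 points | +8.3 points | 54% |

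A person-time rate on the same data is equal in the two arms: about 1.1 per 100 person-months when the control risk is 10%, and about 4.2 when it is 30%.

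**Opposite direction.** Keep hazard ratio 0.7 and add an assumed combination-arm discontinuation hazard of 0.10 per month. The combination window falls to a mean of 6.5 months. A true 1.5-fold event rate then gives 9.9% against 10%, or 30.0% against 30%: a crude difference of about zero.

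**Early-onset events.** Confine the hazard to the first 2 months, equal in both arms, at hazard ratio 0.7. The crude difference is only +0.1 point at 10% control risk and +0.3 at 30%. A person-time rate over the whole window now misleads instead: 1.13 against 0.89 per 100 person-months at 10%, a ratio of 0.79, and 4.27 against 3.39 at 30%, again 0.79. The longer-exposed arm looks about 21% safer although the early risk is identical. Neither summary serves alone.

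**The case against.** The best defence is that the proportion of participants with an event during treatment and its follow-up is a legitimate quantity. The plan does not present it as a risk per unit time. There are no Tier 1 events and no decision rule, and the intervals are declared descriptive. This stands: a reader might infer that the Tier 2 analysis is wrong or its results invalid, and the documents do not support that. It does not answer the point completely, because a descriptive label given for multiplicity does not tell the reader that a difference may reflect observation time.

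Second, the text available is not the whole plan. Only selected safety analyses remain, and they are not listed. The Section 9.6 subsections are kept for reference, and the supplemental SAP may hold further analyses. This also stands, so absence can be stated only for the text available.

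Third, the size is easily overstated. A reader might put a mean window straight into 1 − e^(−λ × time). At 0.05 per month, 6 against 8 months gives 25.9% against 33.0%, a gap of 7.0 points, close to the interval half-width of 7.2 points at 310 per arm. That treats every participant as having the same window. With exponential treatment time plus a 1-month tail and the same means, the figures are 23.9% and 29.5%, a gap of 5.6 points.

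Fourth, a reader might infer that the cycle count merges pembrolizumab-only cycles given after Amendment 007-06 with earlier combination cycles. Section 9.12 does not say so. It refers to study intervention, which Section 6 defines broadly enough to cover each product, and it leaves open whether the drugs are counted separately. Cycles are 21 days, so a count does approximate time.

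**Conclusion.** The point holds as a worthwhile improvement, not as an error in the plan. In the text available, Tier 2 events are compared only as crude proportions, over windows tied to treatment duration, with nothing linking events to time at risk. Under the Section 9.9 PFS assumptions, equal hazards produce about +2.7 to +8.3 points at hazard ratio 0.7 and +1.2 to +3.8 points at 0.85, for control risks of 10% to 50%. Under an assumed early-stopping pattern, a true 1.5-fold rate can show as about zero.

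These figures show that the effect can be material; they do not estimate it in this trial. Observed exposure by arm is not in the documents, the protocol allows treatment beyond first progression, and the removal of lenvatinib and placebo cut some windows short. A reader might infer that the combination's adverse event risk will be overstated, or that it will be hidden; the documents support neither direction. The effect concerns events that accrue over time and is negligible for those confined to the first weeks.

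**What to change.** Keep the crude proportions and their intervals. Add to Section 9.6.2, for the three Tier 2 categories (any adverse event, Grade 3 to 5, serious):

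- Cumulative incidence of first event by arm at fixed times, with death as a competing event, and the between-arm difference with 95% CI. Name the times before the tables are run. Participants whose window closes without an event are censored there; state that this treats closure as uninformative.
- Beside it, exposure-adjusted incidence rates per 100 person-months with 95% CI. Person-time runs from first dose to the earlier of first event and end of the window, with a second version ending when lenvatinib and placebo were removed.

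In Section 9.12, report exposure in months separately for lenvatinib or placebo and for pembrolizumab.

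The cost is one or two extra tables from dosing and event dates already collected, with no change to conduct. The rates assume a roughly constant hazard and mislead for early-onset events, so they should not stand alone. If the supplemental SAP already contains these analyses, a cross-reference from Section 9.6.2 suffices.

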### **Tier 3 Events**

Safety endpoints that are not Tier 1 or 2 events are considered Tier 3 events. Only point estimates by treatment group are provided for Tier 3 safety parameters.

### **Continuous Safety Measures**

For continuous measures such as changes from baseline in laboratory, vital signs, and ECG parameters, summary statistics for baseline, on-treatment, and change from baseline values will be provided by treatment group in table format.

Table 10 Analysis Strategy for Safety Parameters

Safety Tier	Safety Endpoint	95% CI for Treatment Comparison	Descriptive Statistics
Tier 2	Any AE ( $\geq 10\%$ of participants in one of the treatment groups)	X	X
	Any Grade 3 to 5 AE ( $\geq 5\%$ of participants in one of the treatment groups)	X	X
	Any serious AE ( $\geq 5\%$ of participants in one of the treatment groups)	X	X
Tier 3	Any AE		X
	Change from baseline results (laboratory test toxicity grade)		X

Abbreviations: AE = adverse event; CI = confidence interval; X = results will be provided.

### 9.6.3 Statistical Methods for Patient-reported Outcome Analyses

#### Mean change from baseline

The time point for the mean change from baseline will be determined based on blinded data review prior to the database lock for any PRO analysis and documented in the sSAP.

To assess the treatment effects on the PRO score change from baseline in the PRO endpoints defined in Section 9.4.3, a constrained longitudinal data analysis (cLDA) model proposed by Liang and Zeger [Liang, Kung-Yee and Zeger, Scott L. 2000] will be applied, with the PRO score as the response variable, and treatment, time, the treatment by time interaction, and stratification factors used for randomization (See Section 6.3.2) as covariates. The treatment difference in terms of least square (LS) mean change from baseline will be estimated from this model together with 95% CI. Model-based LS mean with 95% CI will be provided by treatment group for PRO scores at baseline and postbaseline time point.

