## 9 STATISTICAL ANALYSIS PLAN

**NOTE: Data from an interim safety and futility eDMC for LEAP-007 (data cutoff: 19-MAY-2021) indicated that the study met the prespecified nonbinding futility criteria for OS for the combination of lenvatinib plus pembrolizumab compared with placebo plus pembrolizumab. This futility analysis was requested at a previous eDMC meeting and conducted as described in the sSAP. Based upon these data and the recommendation of the eDMC, Amendment 007-06 was implemented to unblind the study and remove lenvatinib and matching placebo from the treatment arms. The prespecified interim and final analyses of the study described in the statistical analysis plan (SAP) will not be performed. Selected analyses of safety and ePRO endpoints will be performed at the end of the study; there will be no further analyses of efficacy endpoints.**

This section outlines the statistical analysis strategy and procedures for the study. **As of Amendment 007-06, the study has been unblinded.** Changes made to primary and/or key secondary hypotheses, or the statistical methods related to those hypotheses, that occurred prior to study unblinding were documented in previous protocol amendment(s) (consistent with International Council for Harmonisation [ICH] of Technical Requirements for Pharmaceuticals for Human Use Guideline E9). Changes to exploratory or other nonconfirmatory analyses made after the protocol has been finalized, but before unblinding/final database lock, will be documented in a supplemental statistical analysis plan (sSAP) and referenced in the clinical study report (CSR) for the study. Post hoc exploratory analyses will be clearly identified in the CSR. Separate analysis plans (ie, separate documents from the sSAP) will be developed to detail PK and biomarker analyses. The ePRO analysis plan will be included in the sSAP.

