## 9.2 Responsibility for Analyses/In-house Blinding

**Note: As of Amendment 007-06, the study is unblinded to the Sponsor, the investigational sites, and the participants. This section has been updated accordingly.**

The statistical analysis of the data obtained from this study will be the responsibility of the Clinical Biostatistics department of the Sponsor.

This study was conducted as a double-blind study under in-house blinding procedures until after the eDMC recommended study unblinding.

The Sponsor generated the randomized allocation schedule(s) for study intervention assignment. Blinding issues related to the planned interim analyses are described in Section 9.7, but are no longer applicable as of Amendment 007-06.

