### **9.6 Statistical Methods**

**NOTE: As of Amendment 007-06, the prespecified interim and final analyses of the study will not be performed. Selected analyses of safety and ePRO endpoints will be performed at end of study; there will be no further analyses of efficacy endpoints. The subsections below are retained for reference.**

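### Does the unblinding of the trial undermine the blinded choice of the visit for the PRO change-from-baseline analysis?

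*Combined protocol and SAP*

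**What the plan says.** The PRO change-from-baseline endpoints in Section 9.4.3 cover five scales: global health status/QoL, cough, chest pain, dyspnea and physical functioning. Section 9.6.3 analyses them with a constrained longitudinal model, "with the PRO score as the response variable, and treatment, time, the treatment by time interaction" and the stratification factors as covariates. It reports the least-squares mean difference with a 95% CI. The visit at which that difference is read is not named: "The time point for the mean change from baseline will be determined based on blinded data review prior to the database lock". The same sentence applies this to every PRO analysis and sends the result to the sSAP.

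Section 9.2 covers who analyses the data and under what blinding. On responsibility it states: "The statistical analysis of the data obtained from this study will be the responsibility of the Clinical Biostatistics department of the Sponsor". On the conduct of the trial up to that decision it states: "This study was conducted as a double-blind study under in-house blinding procedures until after the eDMC recommended study unblinding". Its opening note gives the present position: "As of Amendment 007-06, the study is unblinded to the Sponsor, the investigational sites, and the participants".

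The opening of Section 9 says of the futility analysis behind that decision: "This futility analysis was requested at a previous eDMC meeting and conducted as described in the sSAP". It also says "The ePRO analysis plan will be included in the sSAP". The note at the head of Section 9.6 says "Selected analyses of safety and ePRO endpoints will be performed at end of study" and that its subsections are kept for reference. Section 4.2.1.3 records that PRO collection has stopped. In Section 3 the PRO objectives are secondary and, unlike PFS, OS and ORR, have no numbered hypothesis.

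**The concern.** A blinded data review protects an estimate because nobody who picks the visit can see which visit favours which arm. Here the text still speaks of that review in the future tense, while the organisation that would do it has been unblinded and the PRO data set is closed. No section names the visit, dates the review, cites an sSAP version, or assigns the task to staff kept away from the treatment codes. A reader can fairly ask whether the safeguard was used in time.

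If the visit was still open at unblinding and was then chosen with arm-level results in view, the reported difference would be the best of several correlated differences. Its 95% CI would no longer have its nominal coverage. The schedule leaves room for such a choice, because PROs were collected at many visits. With no hypothesis attached, no alpha would be lost. The harm would be to the reading of the PRO estimate and its interval.

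**Working it through.** The plan gives no figure to reproduce on this point. The check is first of the text and then of what would be at stake in the worst case.

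**Text, side by side**

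| Question | What the documents show |
|---|---|
| Where should the visit be recorded? | In the sSAP (Section 9.6.3). The protocol does not undertake to name it. |
| Did an sSAP exist before unblinding? | Yes. It governed the futility analysis (Section 9). Its PRO content is not visible here. |
| Does the future tense show an open choice? | No. Section 9.6 keeps the future tense for PFS, OS and ORR tests that the same note says will not be run. |
| Will mean change be analysed? | Unknown. Only selected PRO analyses are promised, and they are not listed. |
| Were arm-level PRO results seen before the visit was set? | No section says so. Section 9.2 describes access to treatment assignment, not review of PRO results. |

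For bias to arise, three things must hold together: mean change is among the selected analyses, the visit was not fixed before unblinding, and it was then picked on arm-level results. The documents establish none of them.

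**Number of visits.** Section 8.2.2 schedules questionnaires at every cycle to Cycle 17 and every other cycle to Cycle 35. After baseline, Cycles 2 to 17 give 16 visits and Cycles 19, 21, ..., 35 give 9, so 16 + 9 = 25 on-treatment visits. The documents define no shortlist of candidates.

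**Worst case, one scale.** Take k candidate visits with no true effect. The test statistics Z1, ..., Zk are standard normal with correlation ρ between visits, and the largest is reported. The quantity of interest is P(max Z > 1.96), which is 0.025 when k = 1. Values of ρ from 0.4 to 0.8, either equal between all visits or AR(1), are assumptions. So is k.

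For k = 2 two results can be checked by hand:
- Exclusion of zero in either direction is [0.05 − P(both > 1.96)] + P(both < −1.96) = 0.05, because the two joint tails are equal.
- The mean of the larger statistic is √((1 − ρ)/π). This is √(0.6/π) = 0.44 at ρ = 0.4 and √(0.2/π) = 0.25 at ρ = 0.8.

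Simulation with 1,000,000 draws per setting gives:

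| Candidate visits | 95% CI excludes zero, favourable direction | Mean shift of the estimate (SE) |
|---|---|---|
| 1 (fixed visit) | 2.5% | 0 |
| 2 | 3.9–4.7% | 0.25–0.44 |
| 4 | 5.7–8.7% | 0.46–0.88 |
| 6 | 7.0–12.7% | 0.57–1.13 |
| 8 | 7.9–16.4% | 0.64–1.29 |

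**One visit for all five scales.** Section 9.6.3 refers to a single time point for endpoints that span five scales. Optimising one scale alone therefore overstates the effect on a typical scale. If the visit is picked on the average of five scales, with an assumed between-scale correlation of 0.2 to 0.6, the favourable rate per scale is 4.3–7.7% for 4 visits and 5.3–13% for 8. The mean shift for 8 visits is 0.38–1.07 SE.

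**Sensitivity to the assumptions.** If all 25 visits were candidates and a significant result in either direction counted, independence would give 1 − 0.95^25 = 72%. With correlations of 0.5 to 0.9 the figure runs from 66% down to 16%. The size is thus set almost wholly by assumed inputs.

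**When the choice is masked.** If the visit was fixed before unblinding, or is set from completion pooled over arms, the choice does not depend on the treatment differences. The rate stays at 2.5% each way with no shift.

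**The case for a change.** The strongest case for a change is that the text describes a live analysis whose only stated safeguard depends on a blind that has ended. Sections 9.7 and 9.8 are marked as no longer applicable, whereas 9.6.3 is not, and it is the only PRO method in these documents. The existence of an sSAP for the futility analysis does not show that it named a PRO visit. The blinding statement for China in Section 9.2 is in the past tense and sets up no firewall for the end-of-study work. Section 9.6.3 promises least-squares means at a post-baseline time point in the singular, so nothing here commits the sponsor to show every visit. A one-line citation would cost almost nothing.

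Much of that stands. The wording was not updated, and the documents cannot confirm when the visit was chosen. It is reasonable to ask the sponsor for the sSAP version and date. What does not stand is the step from there to a defect in the analysis. The plan puts the visit in a document that is not here, so its absence from the protocol is expected whether or not it was fixed in time. A blinded review does not require the whole department to be blind. It requires that those choosing the visit lack treatment codes or see only pooled completion, and unblinding does not prevent that. By-visit differences can come from the same model through its treatment-by-time term. Section 9.4.3 already leaves supportive PRO analyses to the sSAP, and such a table would not alter the main estimate.

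**Conclusion.** The concern does not call for a change. Section 9.6.3 is legacy wording that points to the sSAP for a detail the protocol was never meant to hold. Carried out as described, the choice of visit gives a sound estimate. A competent analyst would read the visit from the sSAP or, if it was not set there, have staff without treatment codes choose it from pooled completion and say so in the study report. In both cases the error rate stays at 2.5% in each direction.

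The unfavourable figures, about 6% to 16% in the favourable direction for 4 to 8 visits on one scale and about 4% to 13% per scale when one visit serves all five, need three unverified conditions together. They also rest on visit counts and correlations that no document supplies. Little would turn on them: the trial met its OS futility criterion, lenvatinib was withdrawn, no further efficacy analyses will be done, the PRO objectives have no hypothesis, and the time-to-deterioration endpoints do not use the chosen visit. The conclusion assumes that the sSAP contains the PRO plan, as Section 9 says it will. If the sSAP proved silent and the visit had been picked on arm-level results, the PRO estimate would have to be read as post hoc.
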